OMT Trigger Point Protocol Cover Page

Trial Name: Treating Trigger Points: Comparing Muscle Energy Techniques vs. Lidocaine Needling Technique for Pain Control and Quality of Life Measures.

NCT #: NCT05009264

Document Date: April 28, 2022

A comparison of effectiveness of muscle energy technique and dry needling injections on quality of life and pain control in treating trigger points

Introduction

Myofascial pain syndrome is one of the most common musculoskeletal disorders seen in the aging US population ^{1,2}. Its characterized by myofascial trigger points (MTPs) which were first defined by Simons et al. (1999) as hyperirritable nodules in a taut band of skeletal muscle, associated with pain on manual stretching, contraction, or stimulation of the muscle³. Trigger points are further classified into active and latent based on their clinical features ⁴. Active MTPs are characterized by spontaneous pain at rest with referred pain on palpation whereas latent MTPs produce pain on palpation in addition to restriction of range of motion ^{2,4-7}.

Currently, there are a variety of treatment options for MTPs including lidocaine injections, dry needling, osteopathic manipulative treatment, massage therapy, ultrasound therapy etc. There has been a large amount of research investigating the safety and efficacy of dry needling and lidocaine trigger point injection techniques in treating MTPs. The results suggest that dry needling and lidocaine injections were both equally effective in reducing symptoms associated with MTPs as it was the mechanical disruption of the taut fibers due to the needle effect and the depth of adequate penetration that resulted in pain reduction more than the substance actually delivered into the muscle ⁸⁻¹³. Some authors also suggested the importance of a local twitch response (LTR); which is an observable contraction of the taut part of muscle band upon stimulation, during dry needling technique as being pertinent for maximum effectiveness. ^{8,14}However, a recent systemic review found that LTR during dry needling treatment was unnecessary and not required for management of myofascial pain syndrome ¹⁵.

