On the other hand, there has been fewer research investigating the effects of manual treatment on trigger points. Travell and Simons initially treated trigger points with ischemic compression but later changed their recommendation to applying gentle digital pressure to trigger points ¹⁶. A recent study done on traction-compression-stretch technique compared with ischemic compression showed some, albeit minor, increased outcome measures (pain pressure threshold) warranting clinical investigation ⁶. (We can use their comparative model and statistics since it would be similar to our concept) Another study compared active release and muscle energy techniques in treating latent trigger points of the upper trapezius and found that both techniques were equally effective in increasing cervical range of motion and decreasing pain and upper trapezius thickness⁷. Other studies have also shown interest in similar osteopathic manipulative techniques such as counterstrain, myofascial release, facilitated positional release and high velocity-low amplitude thrust techniques in treating trigger points^{3,16-18}.

Studies have showed that the upper trapezius is one of the most common muscles affected by myofascial pain syndrome ^{19,20} leading to referred pain manifesting as headaches and stiff neck.

There is no consensus as to which treatment method is superior, with the decision to treat in a certain way/technique largely based upon the training received by the individual physician rather than the characteristics of the trigger point itself. There are currently no studies evaluating the efficacy of the various treatment options specifically osteopathic manipulative treatment vs. trigger point injections. Thus, the intention of the present study was to determine the efficacy rates of muscle energy techniques vs. dry needling in treating MTPs in the upper trapezius region.

Study Objective

The primary aim of this study is to observe whether osteopathic manipulative treatment or traditional lidocaine/dry needling technique is more efficacious or non-inferior and similar in treating myofascial trigger points in the upper trapezius region as it relates to quality of life and improvement in pain scores.

Study Design

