Pre-intervention assessment will include pain intensity/evaluation using point system and quality of life measured by the neck disability index.

Post-intervention assessment will include pain intensity/evaluation using point system, administered immediately after the intervention, and one week following the intervention using phone survey or online survey depending on patient preference and comfort.

Intervention

Group1 (PCOM): Will receive the muscle energy technique; trigger point isolated followed by post isometric relaxation muscle energy technique

Group 2 (AtlantiCare Regional Medical Center): Will receive lidocaine injection technique

Outcome Measures

1. *Pain intensity*; measured using a point system; where 0 = no pain and 10 = maximum pain. Although this is a subjective measurement by the patient, we are interested in looking at the difference between pre- and post-intervention pain intensity ratings.
2. *Quality of Life*; measured by the Neck disability Index²² which is used to evaluate neck and upper extremity function. The total score is divided by number of answered questions, subtracted 1 and multiplied by 25, in a scale score that range from 0 to 100, with higher scale scores indicating more disability.

Neck Disability Index score rating²³:

- 0-4 points (0-8%) : no disability,
- 5-14 points (10 – 28%) : mild disability,
- 15-24 points (30-48%) : moderate disability,
- 25-34 points (50- 64%) : severe disability,
- 35-50 points (70-100%) : complete disability

Procedure

Patients that consent to the study and are eligible following the inclusion & exclusion criteria will be recruited into the study. They will fill out the pre-intervention survey in the room. Once the survey is completed, the patient will be placed in a seated position and using palpation, the examiner will identify

the MTrP according to the criteria set by Simons et al. Following the subjective pre-assessment, the intervention will be performed.

Group 1 will be primarily focused on patients from the OMM clinic at PCOM. Patients will be administered muscle energy technique of post isometric relaxation as per the Atlas of Osteopathic Techniques on the symptomatic upper trapezius without treatment of surrounding structures by the osteopathic attending physician.

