The outcome measures, reported pain and quality of life, will be analyzed separately using univariate analyses. The differences between the treatment groups across time periods will be analyzed. A two-factor analysis of variance (ANOVA) will be performed for each dependent variable to determine the

difference between treatment groups at the different time points (before the intervention, immediately after the intervention, and a week post the intervention). A 2 x 3 mixed factor design will be used in order to evaluate the between subjects data (intervention type) across the repeated measures (three time periods).

Study Administration

The primary records of data will be in form of pre- and post- intervention surveys. Each survey will contain a random code to link the patient to the survey data and that list will be kept separate from the surveys. All physical copies of data will be stored primarily at [name] office under lock and key with key access only to them. Data collected through Atlanticare pain clinic will be maintained through one set of copies which will be stored at [name] office under lock and key with key access only to them. Data collected through PCOM will be maintained through one set of copies which will be stored at [name] office under lock and key with key access only to them. Surveys administered through email will be sent through a secure link and all online data will be encrypted with access only to principal investigators and research personal. All data obtained through email will be stored on the principal investigator's computer which is password protected. All data and records generated during this study will be kept confidential in accordance with Institutional policies and HIPAA on subject privacy and the investigator and other site personnel will not use the data and records for any purpose other than conducting the study. The identifiers and other data will be destroyed 5 years after study completion in compliance with the Atlanticare Regional Medical Center data retention policy.

References

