- 1 active/latent MTP in the upper trapezius region

The diagnostic criteria to establish myofascial trigger point is adopted from Travell and Simons³ and include:

1. Presence of palpable taut band in the skeletal muscle
2. Presence of hypersensitive tender spot in the taut band
3. Presence of local twitch response upon stimulation of the taut band
4. Reproduction of referred pain upon palpation
5. Presence of spontaneous referred pain pattern

Exclusion criteria: Subjects that exhibited any of the following criteria were excluded from the study:

- Pregnancy or immunocompromise
- Fever/infection
- Previous history of whiplash injury
- Previous history of cervical surgery, cervical radiculopathy, or myelopathy
- Severe disc or cervical lesion
- Evidence of cognitive deficit
- Degenerative or inflammatory disease of the cervical spine or shoulder, fibromyalgia, or neuromuscular diseases
- Use of medications (anticoagulants, anti-inflammatory etc.) or illicit drug use (1 week prior to treatment or follow up)
- Received treatment for MPS a month before the study recruitment

All eligible participants were screened at their respective clinic with the above criteria. Subjects who agreed to participate in the study provided informed consent. At this time, they were given a demographic survey and pre-intervention survey. This survey included a standard pain intensity evaluation using a 0-10 pain scale and a quality-of-life assessment measured by the neck disability index. After enrollment and pre-intervention assessment, the appropriate intervention was administered to

the patient; patients at the Philadelphia OMM clinic received muscle energy treatment, while patients at the Atlanticare Pain Management clinic received lidocaine with dry needling.

Participants presenting to the PCOM OMM clinic were treated with the muscle energy technique of post isometric relaxation on the symptomatic upper trapezius by a board-certified osteopathic physician. After placing patient in a supine position, the shoulder on the affected side was stabilized with one arm. Using the other arm, the head was sidebent contralaterally and rotated ipsilaterally until the restriction barrier was encountered. This position was then maintained for 10 seconds while a normal respiratory rhythm was maintained. After 10 seconds the position was extended further into the barrier and held for 30 seconds and process repeated.

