Participants presenting to the Atlanticare Pain Management clinic received a lidocaine injection after dry needling into the location of the MTP by a board-certified pain management physician. First, the upper trapezius MTP was identified and isolated. After application of a coolant to numb the area, the isolated trigger point was penetrated using a 30-gauge needle, to a depth adjusted depending on the patient, into the subcutaneous tissue. The duration of treatment was approximately 1-2 minutes. Once the myofascial tension was relieved, 2 mL of 0.5% lidocaine was injected into the MTP.

After their respective interventions, the patient completed an immediate post-intervention survey, consisting of a 0-10 pain scale. Finally, approximately 7-10 days after the intervention, patients were contacted by telephone to complete the one-week post-intervention survey consisting of a 0-10 pain scale.

Outcome Measures

Pain intensity; measured using a point system; where 0 = no pain and 10 = maximum pain. Although this is a subjective measurement by the patient, we are interested in looking at the difference between pre- and post-intervention pain intensity ratings.

Data Analysis

The data was analyzed using R software. Values of interest include mean, median, standard deviation, normal distribution, confidence intervals etc. Intergroup and intra-group comparisons were conducted using independent t-tests and paired t-tests, respectively. Alpha level is set at 0.05 and p values less than that will be considered statistically significant. A descriptive analysis of the outcome variables was conducted to compare between the intervention groups. The homogeneity of sociodemographic data (age, sex, comorbid conditions) and outcome measures were analyzed using the Fischer test and Pearson chi square test, respectively.

The outcome measures were analyzed separately in both treatment groups. The contrast between the treatment groups was analyzed. A univariate analysis of the difference of the outcome variables at the different time points (before the intervention, immediately after the intervention, and a week post the intervention) were obtained through the student *t*-tests. A multivariate analysis was carried out using multiple logistic regression models with age, sex, and intervention group (Injection = 0, OMM = 1) factored as the independent variables.

Results

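### The NDI is documented only before treatment, so the Protocol's three-time-point quality-of-life ANOVA cannot be run, and the SAP does not say that this analysis was dropped or why

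*Protocol*

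**What the plan says.** **Aim and analysis (Protocol).** The title is "A comparison of effectiveness of muscle energy technique and dry needling injections on quality of life and pain control in treating trigger points". The Study Objective frames the comparison "as it relates to quality of life and improvement in pain scores". Outcome Measures lists quality of life second, measured by the NDI, and gives no assessment times for it. Data Analysis says "The outcome measures, reported pain and quality of life, will be analyzed separately using univariate analyses" and then "A two-factor analysis of variance (ANOVA) will be performed for each dependent variable". The times are before treatment, straight after it and one week later, in a 2 x 3 mixed design.

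**Schedule (Protocol).** Study Design says "Pre-intervention assessment will include pain intensity/evaluation using point system and quality of life measured by the neck disability index". For later contacts it says "Post-intervention assessment will include pain intensity/evaluation using point system, administered immediately after the intervention, and one week following the intervention", with no mention of the NDI. Procedure adds that the one-week contact asks about pain intensity and reuses the survey given straight after treatment.

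**SAP.** Study Design places "a quality-of-life assessment measured by the neck disability index" in the pre-intervention survey. Afterwards, "the patient completed an immediate post-intervention survey, consisting of a 0-10 pain scale", and the one-week telephone survey is described in the same way. The cover still carries the trial name that mentions quality of life. Outcome Measures lists pain intensity alone, and the Discussion calls pain the primary outcome. Results and Tables 1 and 2 contain no NDI value. Neither Data Analysis nor the limitations paragraph of the Discussion mentions the planned NDI analysis.

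**The concern.** A repeated-measures ANOVA needs the outcome at each time in the model. The Protocol plans one for the NDI but schedules the NDI once, before anyone is treated. A pre-treatment measurement carries no information about what treatment did, so half of a two-part primary aim has no data behind it.

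The SAP then proceeds with pain alone and gives no explanation. A reader who goes from the Protocol to the SAP finds a planned outcome analysis missing and cannot tell whether it was impossible, forgotten or set aside. The Discussion describes the two treatments as equally efficacious and the Conclusion describes them as comparable, without saying that quality of life lies outside those statements.

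**Working it through.** The documents give no NDI sample size, power, effect size or result, so there is no NDI figure to reproduce. The check compares the schedule with the model and counts degrees of freedom.

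**Inputs.** There are 2 groups (Protocol, Intervention) and T = 3 planned times (Protocol, Data Analysis). N = 30 analysed for pain (SAP, Table 2). About 50 evaluable and 60 enrolled were planned (Protocol, Study Design). Actual enrolment was 21 + 10 = 31 (SAP, Results).

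**Formulas for a 2 x T mixed ANOVA.**
- Time df = T − 1
- Group-by-time df = (2 − 1)(T − 1)
- Within-subject error df = (N − 2)(T − 1)

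**Test of the counting rule on the SAP's pain ANOVA.** With N = 30 and T = 3, error df = 28 x 2 = 56, as the SAP prints. The printed numerator df of 1.65 gives a Greenhouse-Geisser factor of 1.65/2 = 0.825 and a corrected error df of 0.825 x 56 = 46.2. F = 3.90 on 1.65 and 46.2 df gives p = 0.034, the printed value. With 56 error df, p would be 0.033.

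**Where the NDI is documented.**

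| Time | Protocol schedule | SAP survey | Cells filled (2 groups) |
|---|---|---|---|
| Before treatment | Pain and NDI | Pain and NDI | 2 of 2 |
| Straight after | Pain | Pain | 0 of 2 |
| One week | Pain | Pain | 0 of 2 |

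The total is 2 of 6 cells.

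**Degrees of freedom for the NDI (group-by-time, error).**

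| NDI times | N = 30 | N = 50 | N = 60 |
|---|---|---|---|
| T = 1 (documented) | 0, 0 | 0, 0 | 0, 0 |
| T = 2 (one later time added) | 1, 28 | 1, 48 | 1, 58 |
| T = 3 (as planned) | 2, 56 | 2, 96 | 2, 116 |

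At T = 1 the factor T − 1 is zero, so the terms vanish whatever N is. What remains estimable is the overall baseline level and the baseline group difference. Adding a one-week NDI would fill 4 of 6 cells and make a one-week contrast estimable, but the three-time model would still need amending.

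**Available baseline NDI.** There are up to 31 values. The one lost patient was lost at one week, after the baseline survey. The number actually collected is not reported.

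**A scoring point to settle before reporting.** The formula in Outcome Measures turns a total of 0 over k answered questions into (0/k − 1) x 25 = −25, although the stated scale runs from 0 to 100. It therefore does not fit the 0-50 point bands printed beneath it.

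**The case against.** **The Protocol may simply have an incomplete schedule.** Its wording on post-intervention assessment does not exclude other instruments, and a three-time ANOVA implies that later NDI was intended. On the Protocol alone this is a fair reading. The Procedure section weakens it, because the one-week contact is about pain. The SAP's description of the surveys actually used settles it.

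**This is a reporting gap that alters no result.** Largely true. The pain analyses do not use the NDI. The SAP's Discussion and Conclusion argue from pain and state no quality-of-life finding. It would also be wrong to say that the SAP hides the outcome, since its cover names quality of life and its Study Design describes the baseline NDI. What is missing is a statement that a planned analysis was not done, and the reason.

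**Stronger readings the documents do not support.**
- A reader might infer that an unfavourable quality-of-life result was withheld once the pain results were known. No post-treatment NDI is documented that could have been withheld, and a pain-only follow-up is already what the Protocol's schedule names. The documents do not date the decision.
- A reader might infer that a complete NDI schedule would have yielded a treatment effect. It would have made group contrasts estimable, no more. Treatment is determined by site. All 21 patients in the muscle energy group are aged 20-29, while 8 of the 10 lidocaine patients are over 60 (SAP, Table 1). Baseline pain averages 2.76 against 7 (SAP, Results).

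**Conclusion.** The point holds. The Protocol's NDI analysis cannot be run on the data that either document describes: 1 of 3 planned times, 2 of 6 cells, and 0 degrees of freedom for time and group-by-time at any sample size. The trial supports no conclusion on the quality-of-life part of its primary aim, and the SAP does not disclose that the planned analysis was dropped or why. The loss is in disclosure and in the scope of the conclusions.

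This rests on one assumption, that the SAP describes its two follow-up surveys completely. If post-treatment NDI values do exist, the survey description needs correcting and the reason for leaving them unanalysed must be given. It needs no assumption about power, effect size or dropout. It should be fixed, but it does not call the reported pain figures into question.

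**What to change.** 1. In the SAP's Data Analysis and limitations, state that the Protocol's NDI ANOVA was not done because the NDI was collected only before treatment, or give the actual reason. Add that the trial supports no conclusion on quality of life, so the statements of equal or comparable efficacy in the Discussion and Conclusion do not extend to it. Cost: a few sentences.
2. Report baseline NDI by group as description only: n, mean, SD and number missing, for up to 31 patients. First reconcile the scoring formula with the 0-50 point bands and say which scale is reported. Cost: one table row from data the SAP says were collected, with no patient contact.
3. If the Protocol is used for further patients, add the NDI to the existing one-week survey and amend Data Analysis to a one-week NDI comparison adjusted for baseline NDI. State that the group contrast would still be confounded with site, age and baseline severity. Cost: one more questionnaire at a contact already planned, and a dated amendment.

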OMT Trigger Point Statistical Analysis Plan Cover Page

Trial Name: Treating Trigger Points: Comparing Muscle Energy Techniques vs. Lidocaine Needling Technique for Pain Control and Quality of Life Measures.

NCT #: NCT05009264

Document Date: August 23, 2022

A comparative study of muscle energy technique and lidocaine injections on treating trigger points

Introduction

Myofascial pain syndrome is one of the most common musculoskeletal disorders seen in the aging US population ^{1,2}. It's characterized by myofascial trigger points (MTPs) which were first defined by Simons et al. (1999) as hyperirritable nodules in a taut band of skeletal muscle, associated with pain on manual stretching, contraction, or stimulation of the muscle³. Trigger points are further classified into active and latent based on their clinical features ⁴. Active MTPs are characterized by spontaneous pain at rest with referred pain on palpation whereas latent MTPs produce pain on palpation in addition to restriction of range of motion ^{2,4-7}. Studies have showed that the upper trapezius is one of the most common muscles affected by myofascial pain syndrome ^{8,9} leading to referred pain manifesting as headaches and stiff neck.

Currently, there are a variety of treatment options for MTPs including lidocaine injections, dry needling, osteopathic manipulative treatment, massage therapy, ultrasound therapy, and pharmacotherapy etc. There have been many studies investigating the safety and efficacy of dry needling and lidocaine trigger point injection techniques in the treatment of MTPs¹⁰⁻¹⁸. It has been demonstrated that both dry needling and lidocaine injections were equally effective in reducing symptoms associated with MTPs; the mechanical disruption of the taut fibers due to the effect of the needle and the depth of adequate penetration resulted in more pain reduction, rather than the substance actually delivered into the muscle ¹⁹⁻²⁴. Some authors also suggested the importance of a local twitch response (LTR); which is an observable contraction of the taut region of the muscle band upon stimulation during dry needling technique, indicating maximum effectiveness of the treatment ^{19,25}. However, a recent systemic review found that LTR during dry needling treatment was unnecessary and not required for management of myofascial pain syndrome ²⁶.

On the other hand, there has been less research investigating the effects of manual treatment on trigger points. Travell and Simons initially treated trigger points with ischemic compression but later changed their recommendation to applying gentle digital pressure to trigger points ²⁷. A recent study exploring the traction-compression-stretch technique (TTCE) compared to ischemic compression showed some, albeit minor, increased outcome measures (pain pressure threshold) warranting clinical investigation ⁶. Another study compared active release and muscle energy techniques in treating latent trigger points of the upper trapezius and found that both techniques were equally effective in increasing cervical range of motion and decreasing pain and upper trapezius thickness⁷. Other studies have also shown interest in similar osteopathic manipulative techniques such as counterstrain, myofascial release, facilitated positional release and high velocity-low amplitude thrust techniques for treating trigger points^{3,27-29}.

There is no consensus as to which treatment method is superior, leaving the method of treatment up to the discretion of the individual physician, rather than the characteristics of the trigger point itself. Often, determination of treatment method is dependent upon the training received by a physician. There are currently no studies evaluating the efficacy of these various treatment options, specifically osteopathic manipulative treatment vs. trigger point injections. Thus, the intention of the present study was to compare the efficacy of muscle energy techniques vs. lidocaine for the treatment of MTPs in the upper trapezius region.

Study Objective

The primary aim of this study is to compare osteopathic manipulative treatment and lidocaine injection technique for treatment of myofascial trigger points in the upper trapezius region.

Study Design

The study is a prospective cohort study containing of participants between ages 25-65 age range that presented to Atlanticare Regional Medical Center pain management clinic and Philadelphia College of Osteopathic Medicine Osteopathic Clinic between November 2021 and February 2022 with trigger point in the upper trapezius muscle.

Inclusion Criteria: Subjects were recruited into the study if they met all of the following criteria:

- Age between 25 and 65 years.
- Previous or current diagnosis of MTP in the upper trapezius region according to the criteria set by Simons et al.³
- 1 active/latent MTP in the upper trapezius region

The diagnostic criteria to establish myofascial trigger point is adopted from Travell and Simons³ and include:

1. Presence of palpable taut band in the skeletal muscle
2. Presence of hypersensitive tender spot in the taut band
3. Presence of local twitch response upon stimulation of the taut band
4. Reproduction of referred pain upon palpation
5. Presence of spontaneous referred pain pattern

Exclusion criteria: Subjects that exhibited any of the following criteria were excluded from the study:

- Pregnancy or immunocompromise
- Fever/infection
- Previous history of whiplash injury
- Previous history of cervical surgery, cervical radiculopathy, or myelopathy
- Severe disc or cervical lesion
- Evidence of cognitive deficit
- Degenerative or inflammatory disease of the cervical spine or shoulder, fibromyalgia, or neuromuscular diseases
- Use of medications (anticoagulants, anti-inflammatory etc.) or illicit drug use (1 week prior to treatment or follow up)
- Received treatment for MPS a month before the study recruitment

All eligible participants were screened at their respective clinic with the above criteria. Subjects who agreed to participate in the study provided informed consent. At this time, they were given a demographic survey and pre-intervention survey. This survey included a standard pain intensity evaluation using a 0-10 pain scale and a quality-of-life assessment measured by the neck disability index. After enrollment and pre-intervention assessment, the appropriate intervention was administered to

the patient; patients at the Philadelphia OMM clinic received muscle energy treatment, while patients at the Atlanticare Pain Management clinic received lidocaine with dry needling.

Participants presenting to the PCOM OMM clinic were treated with the muscle energy technique of post isometric relaxation on the symptomatic upper trapezius by a board-certified osteopathic physician. After placing patient in a supine position, the shoulder on the affected side was stabilized with one arm. Using the other arm, the head was sidebent contralaterally and rotated ipsilaterally until the restriction barrier was encountered. This position was then maintained for 10 seconds while a normal respiratory rhythm was maintained. After 10 seconds the position was extended further into the barrier and held for 30 seconds and process repeated.

Participants presenting to the Atlanticare Pain Management clinic received a lidocaine injection after dry needling into the location of the MTP by a board-certified pain management physician. First, the upper trapezius MTP was identified and isolated. After application of a coolant to numb the area, the isolated trigger point was penetrated using a 30-gauge needle, to a depth adjusted depending on the patient, into the subcutaneous tissue. The duration of treatment was approximately 1-2 minutes. Once the myofascial tension was relieved, 2 mL of 0.5% lidocaine was injected into the MTP.

After their respective interventions, the patient completed an immediate post-intervention survey, consisting of a 0-10 pain scale. Finally, approximately 7-10 days after the intervention, patients were contacted by telephone to complete the one-week post-intervention survey consisting of a 0-10 pain scale.

Outcome Measures

Pain intensity; measured using a point system; where 0 = no pain and 10 = maximum pain. Although this is a subjective measurement by the patient, we are interested in looking at the difference between pre- and post-intervention pain intensity ratings.

Data Analysis

The data was analyzed using R software. Values of interest include mean, median, standard deviation, normal distribution, confidence intervals etc. Intergroup and intra-group comparisons were conducted using independent t-tests and paired t-tests, respectively. Alpha level is set at 0.05 and p values less than that will be considered statistically significant. A descriptive analysis of the outcome variables was conducted to compare between the intervention groups. The homogeneity of sociodemographic data (age, sex, comorbid conditions) and outcome measures were analyzed using the Fischer test and Pearson chi square test, respectively.

The outcome measures were analyzed separately in both treatment groups. The contrast between the treatment groups was analyzed. A univariate analysis of the difference of the outcome variables at the different time points (before the intervention, immediately after the intervention, and a week post the intervention) were obtained through the student *t*-tests. A multivariate analysis was carried out using multiple logistic regression models with age, sex, and intervention group (Injection = 0, OMM = 1) factored as the independent variables.

Results

The study was completed at two primary locations. There were a total of 10 eligible participants from the lidocaine treatment group and 21 eligible participants from the OMM treatment group enrolled after screening for the inclusion and exclusion criteria. 1 subject from the lidocaine treatment group was lost during follow-up at one week post intervention and thus excluded from the per protocol analysis of the study. The remaining participants' data were analyzed in SPSS 26. No significant difference was found between the two groups in regard to sociodemographic data (Table 1). At baseline, the OMM group had a mean pain intensity level of 2.76 (SD 1.8) while the lidocaine treatment group had a mean pain intensity level of 7 (SD 2.8). Descriptive statistics of pain intensity between the two groups demonstrate considerable variance (Table 2).

Within the OMM group, an independent samples t-test found a statistically significant difference between the pre-intervention and immediate post-intervention pain levels, $t(20) = 2.10, p = .048$. The mean pre-intervention pain level ($M = 2.76, SD = 1.84$) was significantly higher than the immediate post intervention pain level ($M = 1.86, SD = 0.96$). An independent samples t-test found a statistically significant difference between pre-intervention and one-week post-intervention pain levels, $t(20) = 2.68 p = .014$. The mean pre-intervention level of pain ($M = 2.76, SD = 1.84$) was significantly higher than one-week post-intervention ($M = 1.81, SD = 2.01$).

Within the lidocaine group, an independent samples t-test did not demonstrate a statistically significant difference between pre-intervention and immediate post-intervention pain levels, $t(20) = 1.17, p = 0.27$. The mean pain level pre-intervention ($M = 7, SD = 2.87$) was higher than immediately post-intervention ($M = 6.60, SD = 2.32$). When evaluating the difference in level of pain from pre-intervention to one-week post-intervention, an independent samples t-test was not statistically significant, $t(20) = 2.16 p = .062$. The mean level of pain pre-intervention ($M = 7, SD = 2.87$) was higher than one-week post-intervention ($M = 4, SD = 2.18$). Pain intensity between the two groups are also demonstrated graphically in Figure 1, with time point one corresponding to pre-intervention, two corresponding to immediately post-intervention and three corresponding to 1 week post intervention.

To investigate the treatment effect between groups across time, a mixed design two factor ANOVA was utilized. As expected, due to small sample size, heterogeneity of covariance matrices was detected. This is considered a limitation of the study. Also, since a repeated measures design was implemented across three time periods, Mauchly's test of sphericity was examined and found to be significant ($p = .042$). This indicates that sphericity cannot be assumed, so a Greenhouse-Geisser statistic was computed. A statistically significant interaction effect was detected, $F(1.65, 56) = 3.90, p = .034$. Due to p-value being less than 0.05, we can confidently reject the null hypothesis and accept the alternative hypothesis.

[figure not shown]
Table 1.

Sociodemographic Data	Mean (SD) or Number (%)		P value
	OMM (n = 21)	Lidocaine (n = 10)	
Sex (%), n = 31 (100%)	21 (100)	10 (100)	
Male, n = 7 (22.6%)	5 (23.8)	2 (20)	
Female, n = 24 (77.4%)	16 (76.2)	8 (80)	
Age, y			
Subjects from 20 – 29 y, n = 22 (71%)	21 (100)	1 (10)	
Subjects from 30 – 39 y, n = 1 (3.2%)	0	1 (10)	
Subjects > 60y, n = 8 (25.8%)	0	8 (80)	
Ethnicity			
Caucasian, n = 20 (64.5%)	11 (52.4)	9 (90)	
African American, n = 1 (3.2%)	1 (4.8)	0	
Latino or Hispanic, n = 4 (12.9%)	3 (14.3)	1 (10)	
Asian, n = 6 (19.4%)	6 (28.6)	0	
Pain Intensity			
Pre-intervention	2.76 (1.8)	7 (2.8)	
Post-intervention (immediate)	1.86 (0.9)	6.6 (2.3)	0.026
Post-intervention (one week)	1.81 (2.0)	4 (2.2)	0.062

Table 2.

	Group	Mean	Std. Deviation	N
Pre-intervention Pain	OMM	2.76	1.84	21
	Lidocaine	7.00	3.04	9
	Total	4.03	2.96	30
Post-intervention immediate pain	OMM	1.86	0.96	21
	Lidocaine	6.56	2.45	9
	Total	3.27	2.66	30
Post-intervention 1 week pain	OMM	1.81	2.01	21
	Lidocaine	4.00	2.17	9
	Total	2.47	2.27	30

Figure 1.

Discussion

The goal of this study was to demonstrate the efficacy of OMT, compared to lidocaine with dry needling injection techniques, in the treatment of trapezius MTP. The results of the study showed that both lidocaine with dry needling and OMT were successful in reducing pain related to myofascial trigger points. However, neither of the two techniques demonstrated discrete superiority to one another. Although, this was not an intent of the study. The primary outcome of interest was pain intensity levels. There was a larger degree of pain reduction in the OMT group immediately post-intervention whereas lidocaine with dry needling showed larger reduction in one-week post-intervention pain levels. In the wake-throes of an opioid epidemic, the search for suitable, effective alternatives that provide non-opioid treatment for pain are an added benefit in patient centered care.

When Travell and Simons first described the concept of myofascial trigger points, they proposed an 'integrated hypothesis' which included local myofascial tissues, genetics, neuromechanical and biochemical factors as precipitating factors in the formation of trigger points^{30,31}. In Travell's ATP energy crisis model³², triggers points were described as focal areas of hypoxia and thus OMT aimed at increasing oxygenation such as gentle traction and pressure release received acceptance. Various studies^{30,32-35} have demonstrated the utility of OMT in treating trigger points. As demonstrated in the results, OMT yielded significant reductions in pain intensity immediately post intervention and one week post intervention. The results of this study are in concordance with other similar studies. Although we hypothesized that OMT would be more as effective as lidocaine for treatment of MTP, we demonstrated that these two treatment methods both provide appropriate relief of musculoskeletal pain. This reflects the validity of OMT in the outpatient clinic, which is a suitable alternative for treatment of MTP. Equal efficacy of OMT for MTP treatment gives patients and physicians the option to elect for a non-invasive, low cost treatment.

